#### **Analysis Populations:**

Safety/Intent to Treat (ITT) population: All subjects who received at least one application of study intervention.

Per Protocol Population: All subjects who completed treatment without major protocol violations affecting the efficacy endpoints.

Protocol PALV-06 Amendment #4

# 27June2022

# 1.2. SCHEDULE OF ASSESSMENTS (SOA)

### Table 2. Schedule of Assessments

	Screening	Baseline Remote	Open-Label Treatment 						
	Visit 1 Screening 		Visit 2 	Blood Draw	Phone Contact	Visit 3	Visit 4	Visit 5	follow-up  Visit 6 Phone contact
Visit Day 	Up to 6 weeks	14-28 days	Day 1	Day 7	Day 14	Day 28	Day 56	Day 84	Day 112
Informed Consent	X	3							
Eligibility Criteria	X		$X^3$						
Med History/ Demographics	X								
Physical Exam	X							X	
Height and Weight	X 							X	
Vital Signs	X		X 			X	X	X	
Clinical Laboratory Tests 	X			X 		X		X	
PK Tests		7				X	X	X	
Urine Pregnancy Test	X	9	$X^3$					X	
CGI-S		3.	$X^3$			X	X	X	
CGI-C		3				X	X	X	
Photography	X	98 9.	$X^3$			X	X	X	

<sup>1 Re-screening is permitted as described in Section 5.5.1

Confidential

<sup>2 Visit window is +/4 days for all visits during the open-label treatment period and Post-treatment follow-up period, excluding Day 1 and 7. Day 1 visit window is +4 days and Day 7 blood draw window is +/- 2 days.

<sup>3 Assessments on Day 1 of OLT should be conducted prior to application of study intervention and are considered part of Baseline

<sup>4 Height is obtained at screening only

<sup>5 Day 7 is sirolimus only and does not need to be fasting.

<sup>6 Fasting labs are required for Visit 3 and Visit 5.

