# Objectives:

Safety Objective:

The primary objective of the study is to evaluate the safety of PTX-022.

Efficacy Objective:

The secondary objective of the study is to evaluate the effectiveness of PTX-022 in treating microcystic LM.

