# **Duration of Participation:**

Each subject will participate in the study for approximately 20 weeks from the time the subject signs the ICF through the safety follow-up period.

**Duration of Study:** The study will require approximately 12 months from the beginning to the end of the study (first subject signing the ICF to last contact with last subject).

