## **Screening Period Inclusion Criteria:**

Participants are eligible to participate in the screening period only if all the following inclusion criteria apply:

- 1) The participant must be at least 6 years of age.
- 2) If less <18 years of age, the participant and legal guardian must provide written informed consent/assent prior to any study procedures.
- 3) The participant must have a clinically confirmed vascular malformation which contains within it a superficial (visible on the skin) microcystic lymphatic malformation (LM).
- 4) The microcystic LM to be treated (lesion) must have a defined total area of
- 5) The participant is willing to abstain from application of other topical medications (prescription or over the counter)
- 6)
- 7) At least have elapsed since the participant has had any major surgery.
- 8) At least have elapsed since the participant has completed therapy with a Growth Factor (GF) that supports platelet, red or white cell number or function.
- 9) Participants must not have received any investigational drug or biologic within whichever is longer, prior to starting treatment with and during treatment with PTX-022.
- 11) The participant is willing to have blood collected for safety and PK testing.

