#### **Baseline Period Inclusion Criteria**

Participants are eligible to participate in the baseline period only if all the following inclusion criteria apply:

- 1) Participant has completed the screening period
- In the Investigator's opinion, the participant's overall health status, including adequate organ function, LDL and cholesterol levels, should be appropriate to permit participation in this clinical trial.
- 3) The participant has adequate Renal Function.
  - a. eGFR>90 mL/min/1.73m^2 or CrC1>90 mL/min

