#### Safety Assessments:

Safety will be assessed through adverse event (AE) evaluations. During the study, subjects will be assessed for the occurrence of new and ongoing AEs. Descriptions of AEs will include the dates of onset and resolution (if resolved), maximum severity, and seriousness, action taken regarding the study drug, corrective treatment, outcome, and the Investigator's assessment of causality. AEs

[figure not shown]
Amendment #4

present at any visit will be followed to resolution (return to normal or to the baseline state) or until clinically stable as determined by the Investigator.

Safety Laboratory Tests: Routine safety laboratory tests (complete blood count/differential urinalysis and serum chemistry) will be performed. Laboratory samples may be obtained from a central or local laboratory facility. Any out-of-range laboratory result that is considered clinically significant by the Investigator will be recorded as an AE and should be confirmed by repeat testing at the discretion of the Investigator. Clinically significant laboratory abnormalities at any visit will be followed to resolution (return to normal or to the baseline state) or until clinically stable as determined by the Investigator.

Physical Examinations: Investigator will evaluate body systems with trial participant.

All Adverse Events will be evaluated using Common Toxicity Criteria for Adverse Events (CTCAE) version TBD at time of final protocol.

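### The schedule requires fasting for both on-treatment safety labs but not for Screening, the only scheduled safety lab before dosing

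*Combined protocol and SAP*

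**What the plan says.** In Table 2 (section 1.2), the Clinical Laboratory Tests row is marked at Screening, Day 7, Day 28 (Visit 3) and Day 84 (Visit 5). It is blank at Baseline Remote and on Day 1. Two footnotes set the fasting conditions. Footnote 6, attached to the row label, reads "Fasting labs are required for Visit 3 and Visit 5". Footnote 5, attached to the Day 7 mark, reads "Day 7 is sirolimus only and does not need to be fasting". Screening is not mentioned in either.

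The synopsis describes the panel under Safety Assessments: "Routine safety laboratory tests (complete blood count/differential urinalysis and serum chemistry) will be performed". It lists no individual analytes and sets no fasting condition. The Baseline Period Inclusion Criteria ask the Investigator to judge the participant's health status, "including adequate organ function, LDL and cholesterol levels, should be appropriate to permit participation in this clinical trial". The supplied text gives no numeric limit for either lipid. On follow-up of abnormal results, Safety Assessments says: "Clinically significant laboratory abnormalities at any visit will be followed to resolution (return to normal or to the baseline state) or until clinically stable".

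**The concern.** The sponsor considers fasting important enough to require it at both on-treatment safety draws. Those values are best read against a pre-dose value taken in the same state, and the schedule does not secure one.

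The stakes come from the design. The Objectives state that "The primary objective of the study is to evaluate the safety of PTX-022", and there is no control arm, so each subject's own pre-dose sample is the only internal comparator. If that sample is unfasted and the later ones are fasted, the change in sampling state is confounded with treatment. For an analyte that runs higher unfasted, the mismatch would tend to hide a rise on treatment. For one that runs lower unfasted, it would tend to create an apparent rise or mask a fall. The same Screening sample is also the only scheduled safety draw available when LDL and cholesterol are weighed for entry to the baseline period.

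**Working it through.** The plan states no figure to reproduce. The check is a reading of the laboratory row against its footnotes, followed by simple counts.

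**Which draws are safety labs, and which must be fasted**

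| Time point | Marked in lab row | Safety panel | Fasting required |
|---|---|---|---|
| Screening (Visit 1) | yes | yes | not stated |
| Baseline Remote | no | – | – |
| Day 1 (Visit 2) | no | – | – |
| Day 7 | yes | no, sirolimus only (footnote 5) | no (footnote 5) |
| Day 28 (Visit 3) | yes | yes | yes (footnote 6) |
| Day 84 (Visit 5) | yes | yes | yes (footnote 6) |

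- Draws marked: 4. Less the Day 7 sirolimus draw: 4 − 1 = 3 safety draws per subject.
- Coverage of the fasting rule: 2 of 3 overall, made up of 2 of 2 on treatment and 0 of 1 before dosing.
- Footnote 3 counts pre-dose Day 1 assessments as Baseline, but the laboratory row has no Day 1 mark. Screening therefore remains the only scheduled pre-dose safety lab.
- No other section of the supplied text requires fasting at Screening.

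**How many subjects could be affected**

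The documents give neither the share of subjects unfasted at Screening nor the size of any fasting effect, so no bias figure can be derived. The schedule as written permits anything from 0 to all of the approximately 10 to 20 dosed subjects to have an unfasted baseline.

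**Burden of extending the rule**

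- Required fasted safety draws now: 2 × 10 = 20 to 2 × 20 = 40.
- With Screening added: 3 × 10 = 30 to 3 × 20 = 60.
- Added: 10 to 20 draws, plus any screen failures.

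**Room for a return draw**

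- Table 2 allows up to 6 weeks of screening: 6 × 7 = 42 days.
- Duration of Participation gives about 20 weeks in total. With 12 weeks of treatment and 4 of follow-up, the pre-dose time is 20 − (12 + 4) = 4 weeks = 28 days.
- Less a Baseline Remote period of 14 to 28 days, this leaves 28 − 14 = 14 down to 28 − 28 = 0 days for screening. The result is approximate because the 20 weeks is approximate.

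**The case against.** The strongest reply is that the footnote is silent on Screening and does not exempt it. Day 7 is expressly released from fasting and Screening is not. The supplied text is only the synopsis and schedule, so a fasting instruction for Screening could sit in the protocol body. This stands as a limit: the documents show that the schedule allows the mismatch, not that it occurs. It does not remove the point, because a site working from Table 2 would find fasting required only at Visits 3 and 5. If the body says otherwise, the footnote still needs to be aligned with it.

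The second reply is that little in the plan depends on the comparison:

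- Statistical Methods promises descriptive summaries but names no laboratory change from baseline or shift table.
- No passage formally defines a laboratory baseline.
- The chemistry analytes are not listed, and LDL and cholesterol appear only as an eligibility judgement.
- Return to the baseline state is one of three end-points for following an abnormal result, beside return to normal and clinical stability.
- Clinically significant out-of-range results become adverse events whatever the baseline was.
- The Visit 3 and Visit 5 values are like for like with each other.

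All of this is right and narrows the reach to fasting-sensitive analytes, in subjects actually unfasted at Screening, when read against Screening. That narrow case is still the natural reading of pre-dose and on-treatment chemistry in an uncontrolled safety study.

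The third reply is that recording fasting status would be enough, without another fasted draw in children as young as 6. Recording does make the mismatch visible and is a reasonable fallback, but it does not supply a comparable baseline.

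**Conclusion.** The concern holds. On the face of Table 2, both on-treatment safety draws are fasted by rule, while the single pre-dose safety draw carries no fasting requirement. The plan should be changed, though the consequence is limited.

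Its size cannot be stated and may be zero. The conclusion rests on two readings: that Screening serves as the laboratory baseline, which follows from its being the only scheduled pre-dose safety lab, and that the panel includes at least some fasting-sensitive chemistry, which the fasting rule itself implies. It also depends on no Screening fasting instruction existing in the protocol body. Confidence is medium for these reasons.

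**What to change.** Extend footnote 6 to the pre-dose safety lab, for example: *Safety laboratory samples are to be drawn fasted at Screening (after consent and within the screening window), at Visit 3 and at Visit 5.* If the protocol body already sets a fasting condition for Screening, bring the footnote into line with it.

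Record fasting status (fasted, not fasted, unknown) at each safety draw, and flag baselines that are unfasted or of unknown status in the laboratory summaries. For subjects already screened, enter unknown unless the status was documented. A separate display of fasted pairs is not needed.

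The cost is one further fasted draw per subject, children included, and one field on the laboratory form. Consent comes first, since "the participant and legal guardian must provide written informed consent/assent prior to any study procedures". Consent and the Screening labs both fall at Visit 1, so some subjects may have to come back for a fasted sample. The screening window in Table 2 has room for this, but the stated participation time is tighter ("Each subject will participate in the study for approximately 20 weeks from the time the subject signs the ICF through the safety follow-up period"), and a return draw could lengthen participation for some. Where a return draw is not feasible, recording fasting status alone still allows the affected baselines to be identified.

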#### Protocol PALV-06 27June2022 Amendment #4

i inchanch na										
Assessment of lesion leakage										
Assessment of lesion bleeding										
Assessment of lesion impact on function										
LM Symptom Severity Scale (Pain)										
LM Symptom Severity Scale (Crusting)		√7								
PGI-SL										
PGI-SB	3									
PGI-CL										
PGI-CB										
Overall PGI-S 			√3			✓	✓	✓		
Overall PGI-C						✓	✓	✓		
DLQI			√3					√ 10		
TSQM								√ 10		
Adverse Events	$X^9$		X	X	X	X	X	X	X	
Application Site Reaction Assessment			X			X	X			
Concomitant Medications	X		X	X	X	X	X	X	X	
Dispense/Collect IP			X			X	X	X		
Accountability/Compliance	25.5		X			X	X	X		
Exit Interview									$X^{12}$	

Palvella Therapeutics, Inc.

<sup>7 Daily in the PDD

<sup>8 Weekly in the PDD

 SAEs will be captured from time of informed consent. AEs not meeting SAE criteria will be captured starting at time of first dose.

<sup>10 Collected after the PGI-S/C

  If parent is completing daily and in-person questionnaires for a child, it should be the same parent completing them throughout the course of the study.
 12 Interviews can occur any time after end of treatment. Interviews will be conducted by an independent, third party. Please refer to the Interview Guide for more information on conduct.

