### Study Design and Duration:

This is an open-label study to evaluate the safety and effectiveness of PTX-022.

The study will consist of a screening and baseline period, 12-week treatment period and 4-week follow up period.

Participants will have 8 visits (remote or on-site) which include:

- Screening
- Day 1 +4 days
- Day 7 (blood draw only done remote or onsite)  $\pm$  2 days
- Day  $28 \pm 4$  days, Day  $56 \pm 4$  days, Day  $84 \pm 4$  days
- Day  $14 \pm 4$  and Day  $112 \pm 4$  (remote)

Number of Study Centers: Approximately 5 sites in the United States

Sample Size: ~10-20 subjects dosed

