# Investigational Product (IP), Dose, Route of Administration, and Regimen:

Test product: PTX-022 (sirolimus) Topical Gel 3.9% w/w

In accordance with study participant safety and tolerability, treatment will be applied according to this administration schedule:

- All subjects shall complete 12 weeks of therapy.
- PTX-022 will be topically administered each day PTX-022 should be applied once daily to the lesion area specific instructions will be available in the Participant Instruction for Use manual. If

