#### **Statistical Methods:**

This is a descriptive, open-label pilot study. Primary and secondary outcomes will be reported by mean or percentage and 95% confidence interval.

All statistical processing will be performed using SAS® or R3.6.1 or later version unless otherwise stated. Summary tables (descriptive statistics and/or frequency tables) will be provided for baseline variables and safety and efficacy variables. Continuous variables will be described by descriptive statistics (n, mean, standard deviation, minimum, median, and maximum). Frequency counts and percentage of subjects within each category will be provided for categorical data.

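### TSQM, post-baseline DLQI and the post-screening physical exam are scheduled only at Day 84, and Table 2 schedules nothing for a participant who leaves early

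*Combined protocol and SAP*

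**What the plan says.** The synopsis (Investigational Product, Dose, Route of Administration, and Regimen) states "All subjects shall complete 12 weeks of therapy" and, in the text available, does not say what is collected from anyone who does not. Under Study Design and Duration it says "Participants will have 8 visits (remote or on-site) which include" and then lists the contacts; none is an early-termination visit.

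Table 2 (Section 1.2) places the relevant measures as follows:

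- TSQM: one mark, at Visit 5 (Day 84).
- DLQI: Day 1 before dosing, and Day 84.
- Physical exam and weight: Screening and Day 84.
- CGI-S/C and Overall PGI-S/C after baseline: Days 28, 56 and 84.

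The Day 84 marks for DLQI and TSQM carry footnote 10, "Collected after the PGI-S/C", which sets the order of questionnaires within the visit. No footnote moves Visit 5 procedures to an earlier stop, and the Day 84 window is 4 days either side.

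Analysis Populations defines Safety/ITT as "All subjects who received at least one application of study intervention" and Per Protocol as "All subjects who completed treatment without major protocol violations affecting the efficacy endpoints". Statistical Methods says "Primary and secondary outcomes will be reported by mean or percentage and 95% confidence interval".

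**The concern.** The two population definitions differ partly in whether treatment was completed, so the plan foresees participants who do not complete it. The schedule provides no end-of-treatment record for them. Followed as written, a participant who leaves before Day 28 contributes no post-baseline CGI or Overall PGI. One who leaves at any time before Day 84 contributes no TSQM, no change in DLQI and no follow-up physical exam.

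If people leave because the gel irritates or does not help, the remaining TSQM and DLQI results will look better than the experience of everyone dosed, although the tables may be labelled ITT. There is no control arm against which to judge this. The values cannot be recovered at the analysis stage.

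**Working it through.** **Schedule check.** The plan gives no figure to reproduce: it states no dropout rate, power or effect size. The first step is to read Table 2 by the time at which a participant leaves the study.

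| Leaves | CGI and Overall PGI after baseline | TSQM, DLQI change, follow-up exam and weight |
|---|---|---|
| Before Day 28 | none | none |
| Day 28 to before Day 56 | Day 28 | none |
| Day 56 to before Day 84 | Days 28 and 56 | none |
| Attends Day 84 | Days 28, 56 and 84 | complete |

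The table concerns leaving the study. A participant who stops the gel but still attends Day 84 belongs in the last row.

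**Weight of one participant.** The sample size is "10-20 subjects dosed". One person is 1/20 = 5% to 1/10 = 10% of the sample.

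**Bounds on a percentage (illustration).** Assume a satisfied/not satisfied summary of TSQM, which the plan does not define, and 20% missing at Day 84. Let N be the number dosed, m the number missing and x the number satisfied among the N − m observed.

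- Observed percentage: x/(N − m).
- Lower bound for all dosed, if every missing person is unsatisfied: x/N.
- Upper bound, if every missing person is satisfied: (x + m)/N.

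With N = 20, m = 4, x = 12: observed 12/16 = 75% (Clopper-Pearson 95% interval 47.6% to 92.7%); bounds 12/20 = 60% and 16/20 = 80%.

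With N = 10, m = 2, x = 6: observed 6/8 = 75% (95% interval 34.9% to 96.8%); bounds 6/10 = 60% and 8/10 = 80%.

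The width of the bounds is m/N, so 10%, 20% or 30% missing gives 10, 20 or 30 percentage points.

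**Shift in a mean (illustration).** If the missing score on average d worse than the observed, the observed mean is too favourable by (m/N) × d. Take d = 1 SD, and compare with the 95% half-width of the observed mean, t(0.975, n − 1)/√n in SD units, where n = N − m.

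| Missing | Shift (SD) | Half-width, N = 20 | Half-width, N = 10 |
|---|---|---|---|
| 10% | 0.10 | 0.50 | 0.77 |
| 20% | 0.20 | 0.53 | 0.84 |
| 30% | 0.30 | 0.58 | 0.92 |

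Under these assumptions the shift is smaller than the sampling error in every row.

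**The case against.** The strongest reply is that the gap is not shown to exist in the full plan. Only the synopsis and schedule are available. Table 2 itself cites a Section 5.5.1 that is not among them, so a protocol body exists and may set discontinuation procedures. This stands: the point can be made only of the synopsis and Table 2.

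Three stronger readings are tempting, and the documents do not support them.

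- A reader might infer that satisfaction and quality of life are measured only in people who stay on the gel. Nothing says that stopping the gel ends participation, so someone off treatment could still attend Day 84. Equally, nothing says that such a person keeps attending.
- A reader might infer that safety follow-up fails for early stoppers. Adverse events are marked at every contact from Day 1 to Day 112 and, under Adverse Event Coding, recorded for 30 days after the last application, a period that moves with an early stop. Vital signs are taken at Days 28 and 56, laboratory tests at Day 28, and a sirolimus level at Day 7. What may be missed is a final exam, weight and laboratory panel.
- A reader might infer a definite inflation of an improvement rate. The plan defines no responder endpoint and does not state a completers-only denominator.

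Other data also soften the loss. Footnotes 7 and 8 refer to daily and weekly diary entries. Most marks in those rows did not survive the PDF reading, so their timing on treatment cannot be judged. The exit interview is not tied to Day 84.

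It is also true that the illustrated bias in a mean is below the sampling error of so small a study. That limits the size of the point but does not remove it, because the 95% interval does not allow for selective missingness.

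**Conclusion.** The point holds as a cheap improvement. In the synopsis and Table 2, TSQM, post-baseline DLQI, the post-screening exam and follow-up weight depend on reaching Day 84, and post-baseline CGI and Overall PGI on reaching at least Day 28, while the ITT population includes everyone with one application.

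The consequence is modest. The study is a descriptive, uncontrolled pilot, and neither TSQM nor DLQI is named as primary. For 10% to 30% missing, bounds on a percentage would span 10 to 30 points, and a mean would shift by 0.1 to 0.3 SD if the missing were 1 SD worse. The missing fractions, the satisfied counts and the 1 SD difference are all assumptions. The conclusion also assumes that the protocol body has no rule; if it has one, what remains is that Table 2 does not point to it.

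**What to change.** Add one footnote to Table 2 or, if the protocol body already has such a rule, a cross-reference to it. The footnote should say that a participant who stops treatment or withdraws before Day 84 has the Visit 5 assessments at the time of stopping: CGI-S/C, Overall PGI-S/C, DLQI, TSQM, physical exam, weight, vital signs, laboratory tests, PK and photography. Application Site Reaction should be listed as an addition, because Table 2 marks it at Days 1, 28 and 56 and not at Visit 5. The footnote should also say whether someone who stops the gel but stays in the study keeps the remaining visits. This concerns data collection only and implies nothing about when treatment should stop.

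In the tables, report these measures with the actual study day and the number observed out of the number dosed. If a display counts missing participants as not improved, show it as a sensitivity result beside the observed-case result.

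The cost is one footnote and one extra contact, using existing forms, for the few who stop early. The drawback is that end-of-treatment values then come from differing days, which is why the day must be shown.
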